9.4.3 ANALYSIS OF THE SECONDARY ENDPOINT(S)

- The difference between the active and sham treatment groups in mean headache intensity during study period

Repeated measures mixed models will be used to describe the difference between the active and sham treatment groups in mean headache intensity during NSCU length of stay. Pain will be modeled as a function of treatment group and measurement time. Subject will be included as a random effect. Least squared means will be used to estimate the treatment effect.

- The difference between total overall morphine equivalence dosage between the active and sham group per subject during study

Total overall morphine equivalence dosage in the active and sham treatment groups will be compared using analysis of covariance (ANCOVA) with adjustment for number of days in study.

-Opiate related adverse events (such as urinary retention, constipation, sedation, nausea, vomiting and pruritis)

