Title: Safety and efficacy of non-invasive Vagus Nerve Stimulation (nVNS) in the treatment of headache in Subarachnoid Hemorrhage (SAH)

MAY, 1, 2022

NCT04126408

Overview of study design

This is a single site, randomized, sham-controlled, double-blind study assessing the feasibility, safety, tolerability, and efficacy of non-invasive VNS (nVNS) in the treatment of headache in subarachnoid hemorrhage (SAH).

We hypothesize that two two-minute noninvasive stimulations of the cervical branch of the Vagus nerve, every 5 hours, is efficacious in safely reducing headache intensity and frequency in patients with headache due to SAH, during the patient's intensive care unit (ICU) stay.

After screening and obtaining informed consent, eligible patients diagnosed with SAH on head scans, admitted to the Neurosurgical Intensive Care Unit (NSCU) at Northshore University Hospital will be randomized to either the treatment (stimulation of the cervical branch of the Vagus nerve) or sham (inactive stimulation) group.

Pain intensity will be evaluated every 4 hours. Non-invasive stimulation will be performed every 5 hours.

The treatment arms are the following:

Group 1: Control (patients will receive treatment using an inactive VNS device)

Group 2: Treatment (patients will receive treatment using an active VNS device)

The patients are randomized with equal probability to one of the treatment arms. In total, approximately 40 patients will be recruited

Primary objective

The primary objective of this study is to evaluate the effectiveness of VNS compared to sham device as measured by the mean daily morphine equivalence dosage during the study

Secondary Objectives

The secondary objectives of the study are to compare VNS to sham treatment with respect to effects on the following:

- total overall morphine equivalence dosage
- mean daily headache intensity during the study
- cytokines levels
- blood brain permeability markers in the blood and/or CSF before and after stimulation
- blood brain barrier integrity

Exploratory objectives:

- stroke, vasospasm, DCI, seizure, and central fever
 - The presence of DCI,
 - Transcranial doppler velocity,
 - The number of days with central fever,
 - Incidence of seizures
- severity of cerebral vasospasm during DSA

Safety objectives:

- Opiate related adverse events (such as urinary retention, constipation, sedation, nausea, vomiting and pruritis)
- Occurrence of Adverse Events (AEs)/Serious Adverse Events (SAEs)
- Vital Signs

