- Rate of side effects:
 - o presence of intolerable pain at the stimulation site,
 - o skin irritation,
 - o nasopharyngitis,
 - o hoarseness,
 - o dysgeusia,
 - o shortness of breath,

Outcome measures

Primary efficacy variable:

The daily morphine equivalency dosage by visit

Secondary efficacy variables:

- total overall morphine equivalence dosage
- mean daily headache intensity during by visit
- cytokines levels
- blood brain permeability markers in the blood and/or CSF before and after stimulation
- blood brain barrier integrity

Exploratory variables:

(Stroke, vasospasm, DCI, seizure, and central fever)

- The presence of DCI,
- Transcranial doppler velocity,
- The number of days with central fever,
- Incidence of seizures)
- severity of cerebral vasospasm during DSA

Safety variables:

Opiate related adverse events

- urinary retention,
- constipation,
- sedation,
- nausea,
- vomiting and
- pruritis
- Occurrence of Adverse Events (AEs)/Serious Adverse Events (SAEs)

Rate of side effects: presence of intolerable pain at the stimulation site,

- skin irritation,
- nasopharyngitis,
- hoarseness,
- dysgeusia,

- shortness of breath,
- Vital Signs (weight, BMI, SBP, DBP, and pulse rate are collected at each day)

Statistical considerations

Sample size determination

There are no statistical hypotheses in this study, and therefore there is no sample size justification for this study. This is a feasibility pilot study that will allow us to better calculate the sample size for a large, randomized control study comparing VNS to sham device.

General approach:

- Baseline is defined as the value measured at visit 1 (Day 1). Endpoint is defined as last observed value during visit 14 (Day 14).
- Missing efficacy. Two statistical approaches to handling missing data will be performed in this study.
 - The primary analysis will be a repeated measures analysis of the primary efficacy endpoint. Estimates have been shown to be unbiased when the missing data are missing completely at random and when there is ignorable nonrandom missing data.
 - A secondary analysis will utilize an LOCF analysis
- All statistical tests for treatment difference will be 2-sided and conducted at the 0.05 level of significance.

Analysis populations

The following analysis sets will be used for the statistical analysis and presentation of data:

- ITT: All randomized participants will be included in the Intent To Treat (ITT) population.

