The primary efficacy variable, the daily morphine equivalency dose by visit, will be analyzed using a restricted maximum likelihood (REML)-based repeated measures approach (Mixed Model Repeated Measures (MMRM)). The model for analysis will include fixed, categorical effects of treatment, visit, and treatment by visit interaction, as well as the continuous, fixed covariates of baseline value. An unstructured (co)variance structure will be used to model the within-patient errors. If this analysis fails to converge, compound symmetry will be tested. The (co)variance structure converging to the best fit, as determined by Akaike's information criterion will be used as the primary analysis. The Kenward-Roger approximation will be used to estimate denominator degrees of freedom. The primary treatment comparison will be the contrast between treatments at Day 14 for active treatment versus sham treatment. Treatment group differences contrasts will be computed overall and for each analysis visit (i.e., Day 1, Day 2, Day 3, ..., Day 14) and displayed with the respective 95% CIs. Significance tests will be based on least-squares means and Type III sum-of-squares, using two-sided tests at the 0.05 level (two-sided 95% confidence intervals). No imputed values will be used for the MMRM analysis.

Sensitivity analysis

All analyses on the primary efficacy endpoint will be repeated on the PPS

Additionally, the missing data for the mean daily morphine equivalency dose will be computed using an LOCF algorithm and analyzed using the MMREM model.

Analysis of Secondary and Exploratory Variables

For each of the variables mentioned above, the randomization group difference will be examined using a T-test for continuous variables, and Fisher's exact test for categorical variables at each visit.

Analysis of safety variables

Treatment group differences in the occurrence of serious adverse events will be evaluated using Fisher's exact test.

Adverse events:

The primary safety endpoint of this study is the overall incidence of device related serious AEs. AEs and SAEs will be summarized and presented as proportions and respective 95% exact binomial confidence intervals (CIs).

Frequency and percentage of subjects experiencing a specific adverse event will be tabulated by system organ class, preferred term, and treatment group.

Summary tables and subject data listings will be provided.

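### Headache intensity has two conflicting analyses: the protocol fits one repeated-measures mixed model, while the SAP assigns a t-test, most likely day by day, and gives no single estimate over the study

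*SAP*

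**What the plan says.** **Protocol 9.4.3.** The group difference "in mean headache intensity during NSCU length of stay" is described by a repeated-measures mixed model. "Pain will be modeled as a function of treatment group and measurement time", with subject as a random effect, and the treatment effect is estimated by least-squares means. No treatment-by-time interaction and no baseline covariate are named.

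**SAP, Analysis of Secondary and Exploratory Variables.** One sentence covers every such variable: the group difference will be "examined using a T-test for continuous variables, and Fisher's exact test for categorical variables at each visit". Under General approach, "All statistical tests for treatment difference will be 2-sided and conducted at the 0.05 level of significance".

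**SAP, definition of the variable.** The Secondary Objectives give "mean daily headache intensity during the study". The list of secondary efficacy variables gives "mean daily headache intensity during by visit".

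**SAP, Efficacy Analysis.** The MMRM (treatment, visit, their interaction, baseline value, unstructured covariance) is set out for daily morphine dose only. The statement "Treatment group differences contrasts will be computed overall and for each analysis visit" belongs to that paragraph and is not extended to headache.

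**Dates.** The SAP is dated May 2022 and the protocol is Version 6 of January 2023. The available text of neither says which prevails.

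**The concern.** Headache is the indication in the title, and the hypothesis in the protocol synopsis and in the SAP overview is that stimulation reduces headache intensity and frequency. The two documents send headache intensity to different analyses that answer different questions. The protocol's model gives one treatment effect. A t-test on each day gives a string of one-day results, each less precise than an average over days, and nothing that summarises the stay.

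Both documents say that the pilot is meant to inform the sample size of a larger trial. For that, one effect estimate with a confidence interval, together with the between-day correlation, is worth more than a list of daily comparisons. If the method stays open, it can also be chosen after the data are seen.

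**Working it through.** The plan gives no effect size, SD or power for headache intensity, so it has no figure to reproduce. The check has two parts.

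**1. The texts side by side**

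| | Protocol 9.4.3 | SAP, daily reading | SAP, single-test reading |
|---|---|---|---|
| Method | Mixed model | t-test per visit | One t-test |
| Quantity tested | Daily scores over the NSCU stay | One day at a time | One value per patient, not defined |
| Overall effect | Yes, the treatment term | None | Yes, but of an undefined summary |

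The grammar allows both SAP readings, because the visit phrase could attach to Fisher's test alone. The variable list, which defines headache by visit, favours the daily reading. The objective, which refers to the whole study, leaves room for the other. Neither reading gives the protocol's model.

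**2. What the difference is worth**

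Inputs from the documents:
- About 40 patients randomised 1:1, so 20 per arm.
- Intervention for up to 10 days (protocol 4.4), with Day 1 as baseline (SAP), so 9 post-baseline days.
- Two-sided 0.05 (SAP).
- Secondary variables analysed in the mITT set only, which requires at least 7 treated days (SAP).

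Assumptions: 80% power, equal variance on each day, complete data, and exchangeable between-day correlation ρ from 0.3 to 0.9. A random subject effect implies exchangeable correlation. With complete data, the 9.4.3 treatment term equals the difference between arms in patients' 9-day means.

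The SD of a 9-day mean, in one-day SD units, is √[(1 + 8ρ)/9]. The one-day standard error relative to that of the mean is its reciprocal.

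The one-day detectable difference is solved from the noncentral t distribution with 2n − 2 degrees of freedom: 0.91 SD at 20 per arm and 1.10 SD at 14 per arm. Multiplying by the SD factor gives the value for the 9-day mean.

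| ρ | SD factor | SE ratio, one day to mean | 9-day mean, 20/arm | 9-day mean, 14/arm |
|---|---|---|---|---|
| 0.3 | √(3.4/9) = 0.615 | 1.63 | 0.56 | 0.68 |
| 0.5 | √(5.0/9) = 0.745 | 1.34 | 0.68 | 0.82 |
| 0.7 | √(6.6/9) = 0.856 | 1.17 | 0.78 | 0.94 |
| 0.9 | √(8.2/9) = 0.955 | 1.05 | 0.87 | 1.05 |

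The 14 per arm illustrates the mITT rule. If stay were normal with mean 8 and SD 2 days (assumed), P(stay < 7) = Φ(−0.5) = 0.31, which leaves 20 × 0.69 ≈ 14.

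If correlation decays with time instead, the ratio is larger at the same ρ: for AR(1) it is 1.15 at 0.9 and 1.50 at 0.7.

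**The case against.** **The comparisons are descriptive.** The protocol calls the secondary endpoints descriptive, and both documents say that there are no statistical hypotheses. This stands. A reader might infer that the daily tests inflate a type I error rate that the trial must control. The documents do not support that, because no confirmatory claim rests on headache intensity. The SAP's 0.05 rule does mean that daily p-values would be produced, and one day could be singled out. That is a matter of presentation.

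**The precision gain may be small.** This also stands in part. At a correlation of 0.9 the one-day standard error is only 5% larger. Much larger ratios are possible under steeply decaying correlation, for example 2.29 for AR(1) at 0.3. That pattern leaves almost no stable patient effect and fits poorly with the protocol's random subject term, so the conclusion does not rely on it.

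**The SAP may intend one test.** It may, and the text does not exclude it. But the per-patient value is not defined (which days count, how short stays are handled), and the method still differs from the protocol's.

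**One document may already prevail.** A reader might infer from the dates that the later protocol overrides the SAP, or that the SAP overrides as the more detailed plan. Neither inference is supported by the text available. Title and signature pages are not available, so the claim goes no further than that.

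**Conclusion.** The conflict is real on either reading of the SAP and depends on no calculation. As the SAP most likely reads, it gives no single estimate of the effect on headache intensity over the study. The cost is precision. Under the stated assumptions, a one-day standard error is about 1.05 to 1.63 times that of the 9-day mean. At 80% power the detectable difference is 0.91 SD against 0.56 to 0.87 SD at 20 per arm, or 1.10 SD against 0.68 to 1.05 SD if mITT leaves about 14 per arm. The correlations, complete data and mITT size are assumptions, since the documents give none of them.

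This should be corrected before analysis, but it does not threaten the trial. It concerns a descriptive secondary endpoint in a pilot.

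**What to change.** In the SAP:

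1. Take headache intensity out of the sentence that assigns t-tests by visit, and specify one repeated-measures mixed model in full. There are two acceptable forms:
   - The protocol 9.4.3 model: treatment, day and a random subject effect. Its treatment term, with a 95% CI, is the single overall effect.
   - The form of the SAP's primary MMRM. In that case state that the treatment-by-visit interaction, the Day 1 covariate and the covariance structure depart from 9.4.3. Define the overall contrast as the equally weighted average over named post-baseline days, because the SAP gives no weighting.
2. State the window. Protocol 9.4.3 models the NSCU stay, whereas the endpoint covers the study period and protocol 8.1 also records daily headache on the floor after ICU discharge.
3. Show per-day differences descriptively, with 95% CIs and no p-values. They must come from the interaction model or from simple daily summaries. The 9.4.3 main-effects model assumes the same difference every day and cannot supply them.

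The cost is SAP wording and a short model specification; the second form can adapt the primary analysis code. No new data are needed, since headache scores are already collected. The same SAP sentence also conflicts with the protocol's method for total morphine dose, which should be handled as a separate point.

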3 OBJECTIVES AND ENDPOINTS

The primary outcome measurement for effectiveness is:

-The difference between the active and sham treatment groups in mean daily morphine equivalence dosage during study

Secondary endpoints include descriptive comparisons between the active and sham treatment groups in:

- The difference in mean daily headache intensity during the study

The difference between total overall morphine equivalence dosages per subject during study
 Opiate related adverse events (such as urinary retention, constipation, sedation, nausea, vomiting and pruritis)

- The difference in cytokines levels and brain permeability markers in the blood and/or CSF before and after stimulation and between the sham and active device group

- Effects of VNS on brain permeability measured through CT perfusion studies

-The difference in modified rankin scale at hospital discharge and during outpatient follow up. This will be collected retrospectively from the follow up outpatient visit.

Exploratory analyses will include descriptive comparisons of the rates of stroke, vasospasm, DCI, seizure, central fever and severity of vasospasm between the active and sham treatment groups.

OBJECTIVES	ENDPOINTS
Primary Objective:	

Incidence of device related serious adverse events.	Proportion of patients with device related adverse events
The difference between the active and sham treatment groups in mean daily morphine equivalence dosage during study	Morphine equivalence dosage will be calculated per day.
Secondary Objectives	
The difference between the active and sham treatment groups in the mean daily headache intensity during the study	Headache intensity will be measured throughout the day and a mean daily headache intensity will be calculated.
The difference between total overall morphine equivalence dosage between the active and sham group per subject during study	Total morphine equivalence dosage for the duration of the study will be calculated.
Incidence of opiate related adverse events (such as urinary retention, constipation, sedation, respiratory depression, nausea, vomiting and pruritis)	Number of patients with of urinary retention, constipation, sedation, nausea, respiratory depression, vomiting and pruritis.

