The difference in cytokines levels and blood brain permeability markers in the blood and/or CSF before and after stimulation and between the sham and active group	When possible, cytokines levels and permeability markers will be measure in the blood and/or serum just before the first vagus nerve stimulation and approximately 24 hours later, after the 11:30 AM stimulation session. If possible, this will be repeated on day 5 and 7 post-ictus as it is the period of cerebral vasospasm

	Immunologic investigations include but not limited to, measurement of inflammatory protein levels, RNA		
	sequencing of leukocyte and stimulation assays.		
Evaluate the effects of VNS on	The integrity of the blood brain barrier will be evaluated		
blood brain barrier integrity	through CT perfusion if performed as standard of care.		
Exploratory objectives			
Comparisons of the rates of stroke, vasospasm, DCI, seizure, and central fever between the active and sham treatment groups	Neuroimaging upon admission and at discharge will be compared and evidence of new strokes will be noted. The presence of DCI (change in neurologic examination thought to be due to vasospasm) will be evaluated.		
	Transcranial doppler velocities will be compared between the active and sham groups		
	The number of days with central fever will be compared between the active and sham groups		
	Incidence of seizures will be compared between the active and sham groups		
Effect of nVNS on severity of cerebral vasospasm during DSA	Rate of change in the severity of cerebral vasospasm will be noted before and during or after nVNS		

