4.4 END OF STUDY DEFINITION

The study intervention will be up to 10 days in length. Vagus stimulation will be performed 4 times daily (approximately at 6:30AM, 11:30AM, 4:30PM and 9:30PM). Data collection will continue till hospital discharge. If the participant becomes hemodynamically unstable, defined as hypotension requiring vasopressors the VNS will be held for safety purposes. However, it will be resumed, once the patient is stabilized, off vasopressors for 48 hours. If the patient is being hemodynamically augmented for symptomatic vasospasm, n-VNS will not be withheld as the beneficial effects of n-VNS on symptomatic vasospasm will be investigated in this study.

Participants must fulfill all of the inclusion criteria in order to be eligible for the study:

- Established signed and dated informed consent form
- Can be enrolled within 5 days of cerebral aneurysm treatment.
- CT of the head revealing blood in the subarachnoid space
- Subject has ruptured cerebral aneurysm or SAH patients who do not have vascular malformation on cerebral angiogram.
- Subject is male or female 18 -75 years of age
- Subject is alert able to verbalize pain at the time of enrollment
- Subject reports pain of 7 and greater on a 10 Point Pain numeric rating scale or presenting with severe headache.
- Female of reproductive age must have a negative pregnancy test (Urine or blood test)

nVNS will only be performed if vital signs are stable (HR>60, SBP> 100 mmHg, MAP> 60 mmhg, and saturation > 90% on room, nasal cannula or face mask). Then the vagus nerve will be stimulated.

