9 STATISTICAL CONSIDERATIONS

9.1 STATISTICAL HYPOTHESES

There are no statistical hypotheses in this study. This is a feasibility pilot study that will allow us to better calculate the sample size for a large randomized control study comparing VNS to sham device.

The primary outcome measurements for effectiveness will be:

-The difference between the active and sham treatment groups in mean daily morphine equivalence dosage during the study period

Secondary endpoints include descriptive comparisons between the active and sham treatment groups in:

- The difference between the active and sham treatment groups in mean daily headache intensity during the study period

- The difference between total overall morphine equivalence dosage between the active and sham group per subject during study

-Opiate related adverse events (such as urinary retention, constipation, sedation, nausea, vomiting and pruritis)

Exploratory analyses will include comparisons of the rates of stroke, vasospasm, DCI, seizure, central fever and severity of vasospasm between the active and sham treatment groups.

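### The SAP covers seizure, DCI, vasospasm and stroke with one per-visit Fisher rule and specifies no per-patient comparison of their rates

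*SAP*

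**What the plan says.** **Protocol.** Section 3 states that "Exploratory analyses will include descriptive comparisons of the rates of stroke, vasospasm, DCI, seizure, central fever" (and severity of vasospasm) between arms. The objectives table in the same section repeats the aim as "Comparisons of the rates of stroke, vasospasm, DCI, seizure, and central fever between the active and sham treatment groups" and adds "Incidence of seizures will be compared between the active and sham groups". In that table, new stroke comes from setting discharge neuroimaging against admission neuroimaging, which gives one reading per patient. Section 9.1 repeats the aim: "Exploratory analyses will include comparisons of the rates of stroke, vasospasm, DCI, seizure, central fever and severity of vasospasm". Section 9.4 gives no analysis method for these events.

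**SAP.** The exploratory variables include the incidence of seizures and "The presence of DCI", with no time window for either. Under Analysis of Secondary and Exploratory Variables, the whole method is a t-test or, for categorical data, "and Fisher's exact test for categorical variables at each visit". The only list of visits is in the description of the primary mixed model, which refers to "each analysis visit (i.e., Day 1, Day 2, Day 3, ..., Day 14". The protocol's section 4.4 says "The study intervention will be up to 10 days in length".

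Elsewhere the SAP names Fisher's exact test without the per-visit phrase: for baseline comparisons under Patient characteristics, and for serious adverse events under Analysis of safety variables.

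**The concern.** A comparison of event rates is normally the proportion of patients in each arm who have the event at least once. A test at each visit answers a different question unless the visit's value is cumulative: whether the arms differ on that day, among patients still observed. Seizure and DCI onsets are likely to be scattered over the stay, so daily tables could hold few or no events, and the daily denominators shrink as patients are discharged.

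Two things are at stake. A row of daily p-values near 1 could be read as absence of effect on secondary brain injury, which protocol section 2.3.1 gives as a reason for including aneurysmal patients. And the pilot is meant to help size a larger trial, which needs per-patient rates with their uncertainty.

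**Working it through.** The documents give no event rate, power or sample size basis for these outcomes, so there is no figure to reproduce. The calculation below only sizes the issue.

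**Inputs from the documents.** About 40 patients with equal allocation, so 20 per arm (SAP, Overview of study design); two-sided tests at 0.05 (SAP, General approach); Fisher's exact test.

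**Assumptions.** Proportion ever affected in each arm; onset uniform over Days 1 to 10; nobody discharged; the event scored for k days from onset.

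**Formula.** On a day when the full k-day window can contribute, the chance that a patient is scored positive is p × k/10, where p is the proportion ever affected. Power is the sum, over all counts a (sham) and b (active), of Bin(a; 20, p_sham × k/10) × Bin(b; 20, p_active × k/10), taken where the Fisher p-value is at most 0.05. With k = 10 (carried forward to Day 10) this is the per-patient test.

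**Hand check for 40% vs 10%, onset-day scoring.** The daily chances are 0.40/10 = 0.04 and 0.10/10 = 0.01. With no event in the other arm, significance needs at least 5 events against 0 (5/20 vs 0/20, p = 0.047; 4 vs 0 gives 0.106).
- P(5 sham) = 15504 × 0.04^5 × 0.96^15 = 0.00086
- P(6 sham) = 38760 × 0.04^6 × 0.96^14 = 0.00009
- P(0 active) = 0.99^20 = 0.818
- (0.00086 + 0.00009) × 0.818 ≈ 0.0008, or about 0.1%

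**Exact power of the best single day:**

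| Ever affected, sham vs active | Onset day only | 3 days | 5 days | Carried forward = per-patient test |
|---|---|---|---|---|
| 40% vs 10% | 0.1% | 4.7% | 16.8% | 49.2% |
| 50% vs 10% | 0.2% | 10.0% | 29.9% | 74.2% |
| 30% vs 10% | 0.02% | 1.6% | 7.0% | 24.2% |
| 20% vs 5% | 0.003% | 0.4% | 2.7% | 16.8% |

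**Any of 14 daily tests significant** (simulation, 40% vs 10%): about 0.8%, 25%, 47 to 48%, and 56% for the four scorings. With 30% in both arms and carried-forward scoring, the chance of at least one false positive among the 14 is about 7%, against 2.5% for the single per-patient test.

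**Illustration, deliberately extreme.** Seizures in 10/20 sham and 0/20 active patients give p = 0.0004 per patient. If each falls on a different day, every daily table is 1 vs 0 or empty and no daily p-value is below 1.0.

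**Stroke.** No arithmetic is needed. One admission-to-discharge reading per patient has no daily values to test.

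**The case against.** The strongest reply is that the per-visit rule cannot be meant literally for every variable it covers. Total morphine dose and the number of days with central fever have one value per patient. The SAP's list of outcome measures attaches a by-visit label to daily morphine dose and headache intensity but not to seizure or DCI. A sensible analyst might therefore compare seizure and DCI once per patient. The Day 1 to Day 14 list belongs to the mixed model, and the SAP's schedule table has only four phases.

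This stands in part. A reader might infer that the SAP tests single-day prevalence and never compares per-patient rates. The documents do not support that: they leave the visit value undefined, and a cumulative value at the last visit would be the per-patient comparison. A reader might also infer that the trial cannot show an arm difference in these events. That is close to true only for onset-day scoring. With longer scoring, some daily test reaches significance in about a quarter to a half of trials under 40% vs 10%, though no visit is named as decisive. For stroke, a test at discharge would be the per-patient comparison among those imaged, so the rule misfits stroke rather than destroying its analysis.

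It is also fair that protocol section 3 calls these comparisons descriptive, that there are no statistical hypotheses, and that the per-patient test is itself weak at moderate differences (17% to 24% in the lower rows of the table). This limits the weight of the point. It also favours estimates over a series of tests at the 0.05 level.

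The adverse event table, which counts subjects per event by arm, is only a partial substitute. Protocol section 8.3.3 asks for all events to be documented, but section 8.3.4 limits reporting of expected SAH complications to those that are device-related or unexpected. The underlying data are recorded, so the rates could still be recovered; the plan simply does not call for them.

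**Conclusion.** The point holds as a gap between objective and method. The only stated test for these events is per visit, no per-patient comparison is specified, and the visit value is undefined. Under 40% vs 10%, with 20 per arm and onset uniform over Days 1 to 10, the best single day has about 0.1%, 5% or 17% power for 1, 3 or 5 days of scoring, against 49% per patient. The loss disappears only if the value is carried forward, which the SAP does not say: its last-observation-carried-forward rule is written for the morphine dose analysis. Event rates, onset pattern and scoring length are all assumptions, and the size of the loss depends on them. Because these are exploratory endpoints in a pilot without a powered hypothesis, the consequence is confined to how the rates are reported and carried into planning the larger trial. It should be corrected, but it does not touch the primary result.

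**What to change.** In the SAP, take stroke, vasospasm, DCI and seizure out of the per-visit rule. For each:

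- Define one yes/no value per patient: at least one event from randomisation to the end of the study period. For stroke, use new stroke on discharge versus admission imaging. For vasospasm, state which recorded finding counts, since the listed measures are Doppler velocity and angiographic severity.
- Report the proportion by arm as randomised, with the risk difference and its 95% CI. Give Fisher's p-value only as a supplement.
- Name the analysis set, because the SAP assigns none to exploratory variables. Examples are all randomised patients counted from randomisation, or the safety set counted from first stimulation. The start of counting must match the set.
- State the end of the window. The Day 14 grid and the protocol's period of up to 10 days need to be reconciled first.
- Keep counts by day as a descriptive table without tests.

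The cost is SAP wording and one explicit choice of population; no new data are needed. The small downside is that a difference confined to part of the stay is described rather than tested.
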